9.6. Analysis of demographics

- The demographic characteristics (age in years at challenge dose, gender, geographic ancestry, height, weight and BMI) at Visit 1, cohort description and withdrawal status will be summarised using descriptive statistics. The same analysis will be performed stratified by age. The age stratification will be 40-50 and 51-60 years.

- Mean, median and standard deviation will be provided for continuous variables such as age.
- Frequency tables will be generated for categorical variables such as gender, race and centre.

9.7. Analysis of immunogenicity

The primary analysis on the response to the challenge dose will be performed on the ATP cohort for analysis of immunogenicity. If the percentage of subjects excluded from the ATP cohort for immunogenicity is more than 5%, a second analysis based on the TVC will be performed to complement the ATP analysis of immunogenicity. The immunogenicity analysis based on the TVC will include subjects for whom immunogenicity data are available. All the immunogenicity analysis will be performed as a whole group and by age stratification. The age stratification will be 40-50 years and 51-60 years.

The following analyses will be performed:

- The percentage of subjects with anti-HBs antibody concentrations ≥ 6.2 mIU/ml, ≥ 10 mIU/ml, ≥ 100 mIU/ml, ≥ 1000 mIU/ml with exact 95% CIs will be calculated at the pre-challenge dose time-point, Day 7 and Day 30 post-challenge dose time-points.
- The percentage of subjects who mount an anamnestic response to the challenge dose, one month after vaccination, will be tabulated with exact 95% CI as a whole and according to their seroprotection status at pre-challenge time-point (anti-HBs antibody concentrations \leq or ≥ 10 mIU/ml).
- GMCs with 95% CI will be calculated for anti-HBs antibodies at the pre-challenge dose time-point, Day 7 and Day 30 post-challenge dose time-points.
- The distribution of anti-HBs antibody concentrations will be displayed using reverse cumulative distribution curve (RCC) at the pre-challenge dose time-point and Day 30 post-challenge dose time-point.
- Relationship between pre-challenge dose time-point and Day 30 post-challenge dose time-point results will be presented by regression line graph.
- CMI responses in terms of frequency of HBs-specific CD4 $^{+}$ T-lymphocytes and frequency of HBs-specific memory B cells at Day 0, Day 7 and Day 30 (for subjects who received a challenge dose) will be evaluated.
- The percentage of subjects with anti-HBs concentrations ≥ 6.2 mIU/ml, ≥ 10 mIU/ml and ≥ 100 mIU/ml (with 95% CI) at the Day 7 and Day 30 post-challenge dose time-points will be tabulated in relation to their pre-challenge dose status (overall, < 10 mIU/ml and ≥ 10 mIU/ml).
- The percentage of subjects (with 95% CI) who mount an anamnestic response will be calculated and in relation to their pre-challenge dose status (< 10 mIU/ml and ≥ 10 mIU/ml).

9.8. Exploratory Analysis:

- Correlation between the anti-HBs specific T and memory B cells (frequency of cytokine-positive CD4⁺ or T-lymphocytes and frequency of memory B cells) with the amplitude of anamnestic response one month after the challenge dose will be analysed by Pearson's correlation coefficient.
- Further logistic regression modelling will be used to assess the impact of prognosis factors like age, gender, geographic ancestry, BMI and pre-vaccination status (seroprotected or not) on the seroprotection rate after the challenge dose. Actual age and BMI at the time of screening will be considered in the model.

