9.5. Derived and transformed data

- Seronegative subjects:
 - Subjects with anti-HBs antibody concentration < 6.2 mIU/ml
- Seropositive subjects:
 - Subjects with anti-HBs antibody concentration ≥ 6.2 mIU/ml
- Seroprotected subjects:
 - Subjects with anti-HBs antibody concentration ≥ 10 mIU/ml

- Anamnestic response to the challenge dose is defined as:
 - At least (i.e. \geq) 4-fold rise in one month post-vaccination anti-HBs antibody concentrations in previously seropositive subjects.
 - In previously seronegative subjects, anti-HBs antibody concentrations ≥ 10 mIU/ml at one month post-challenge dose time-point.
- Amplitude of anamnestic response is the change in fold value from pre-challenge dose time-point to one month post-challenge dose.
- GMC calculations are performed by taking the anti-log of the mean of the \log_{10} concentration transformations. GMC will be calculated on all subjects. Antibody concentrations below the cut-off of the assay will be given an arbitrary value of half the cut-off for the purpose of GMC calculation.
- For a given subject and a given immunogenicity measurement, missing or non-evaluable measurements will not be replaced. Therefore, an analysis will exclude subjects with missing or non-evaluable measurements.

Safety/Reactogenicity:

For the analysis of solicited symptoms within 4 days (Days 0-3) post-challenge dose, missing or non-evaluable measurements will not be replaced. Therefore, the analysis of the solicited symptoms based on the TVC will include only subjects with documented safety data (i.e. symptom screen completed).

More specifically, the following rules will be used:

- Subjects who documented the absence of a solicited symptom after challenge dose will be considered not having that symptom after that dose.
- Subjects who documented the presence of a solicited symptom and fully or partially recorded daily measurement over the solicited period will be included in the summaries at the challenge dose and classified according to their maximum observed daily recording over the solicited period.
- Subjects who documented the presence of a solicited symptom after the challenge dose without having recorded any daily measurement will be assigned to the lowest intensity category at that dose (i.e. 37.5°C for fever or grade 1 for other symptoms).
- Doses without symptom sheets documented will be excluded.

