- Correlation between the anti-HBs specific T and memory B cells (frequency of cytokine-positive CD4⁺ or T-lymphocytes and frequency of memory B cells) with the amplitude of anamnestic response one month after the challenge dose will be analysed by Pearson's correlation coefficient.
- Further logistic regression modelling will be used to assess the impact of prognosis factors like age, gender, geographic ancestry, BMI and pre-vaccination status (seroprotected or not) on the seroprotection rate after the challenge dose. Actual age and BMI at the time of screening will be considered in the model

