Template 17 Anamnestic Response for Anti-HBs antibody concentrations in relation to their pre vaccination status (ATP cohort for immunogenicity)

| | | | Anamnestic response to the challenge dose | | | | |
|-----------|---------------------------|--|---|---|--------|----|----|
| | | | | | 95% CI | | |
| Group | Pre-vaccination status | | N | n | % | LL | UL |
| HBV Group | < 6.2 mIU/mL | | | | | | |
| | ≥ 6.2 mIU/mL - <10 mIU/mL | | | | | | |
| | ≥ 10mIU/mL | | | | | | |
| | Total | | | | | | |

HBV : Engerix-B challenge dose

S- = seronegative subjects (antibody concentration < 6.2mIU/mL for anti-HBs) prior to vaccination

S+ = seropositive subjects (antibody concentration ≥ 6.2mIU/mL for anti-HBs) prior to vaccination

Total = subjects either seropositive or seronegative at pre-vaccination

Challenge Dose response defined as:

For initially seronegative subjects, antibody concentration greater than or equal 10mIU/mL (≥10mIU/mL)

For initially seropositive: antibody concentration at least four times the pre-vaccination antibody concentration

N = number of subjects with both pre- and post-vaccination results available

n(%) = number(percentage) of responders

95% CI = exact 95% confidence interval; LL = lower limit, UL = upper limit

Template 18 Percentage of subjects with positive anti-HBc antibody concentrations at baseline (ATP cohort for immunogenicity)

| | | 95%CI | | | | | |
|----------------------------|-----------|----------|---|---|---|----|----|
| Antibody | Group | Timing | N | n | % | LL | UL |
| Positive Anti-HBc antibody | HBV group | Baseline | | | | | |

HBV : Engerix-B challenge dose

GMC = geometric mean antibody concentration calculated on all subjects

N = number of subjects with available results

n/% = number/percentage of subjects with concentration within the specified range

95% CI = 95% confidence interval; LL = Lower Limit, UL = Upper Limit

Template 19 Correlation between the anti-HBs specific T and memory B cells (frequency of cytokine-positive CD4+ or T-lymphocytes and frequency of memory B cells) with the amplitude of anamnestic response one month after the challenge dose by Pearson's correlation coefficient (ATP cohort for immunogenicity)

| | | 95% CI | |
|-----------|-----------------------------------|--------|----|
| Stimulant | Pearson's correlation coefficient | LL | UL |
| | | | |
| | | | |
| | | | |
| | | | |
| | | | |

Stimulant: anti-HBs specific T and memory B cells

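### The exploratory correlation of T-cell and memory B-cell frequencies with fold rise in anti-HBs is not adjusted for the pre-challenge level and may be biased downward; adding a baseline-adjusted line costs almost nothing

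*Protocol*

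**What the plan says.** Protocol 9.5 and SAP 11.2.4 share one definition: "Amplitude of anamnestic response is the change in fold value from pre-challenge dose time-point to one month post-challenge dose". Protocol 9.8 then states that the association of cell frequencies "with the amplitude of anamnestic response one month after the challenge dose will be analysed by" Pearson's correlation coefficient. SAP 6.3.1 repeats it: "frequency of memory B cells) with the amplitude of anamnestic response one month after the challenge dose will be analysed by Pearson's correlation coefficient". The shell for the result, Template 19 in SAP Annex 3, has columns only for stimulant, coefficient and 95% CI, with the footnote "Stimulant: anti-HBs specific T and memory B cells".

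Nothing else in the plan brings the pre-challenge level into this analysis:

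- Protocol 9.7 and SAP 6.3.1 repeat all immunogenicity analyses by age stratum, but not by pre-challenge level for this correlation.
- The pre-challenge level against Day 30 is a graph only: "Relationship between pre-challenge dose time-point and Day 30 post-challenge dose time-point results will be presented by regression line graph".
- The logistic model in Protocol 9.8 does use "pre-vaccination status (seroprotected or not) on the seroprotection rate after the challenge dose", but its outcome is seroprotection and cell frequencies are not among its listed factors.
- SAP 6.3.2 (additional considerations) and SAP 9 (changes from planned analyses) are both marked not applicable.

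Three details are also open. No log scale is stated for the correlation. The half-cut-off value is given for GMC calculation only, not for the fold-rise denominator. Cells are measured at Day 0, Day 7 and Day 30, and the text does not say which time-point is correlated.

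**The concern.** The outcome is a ratio with the pre-challenge concentration as its denominator. Pre-challenge antibody and memory-cell frequency may well be related, since both are remnants of the same primary series. If they are, and if subjects who start high rise proportionally less, then subjects with more memory cells tend to show smaller fold rises simply because they start higher. The unadjusted coefficient mixes that effect with the association between cells and booster response at a given starting level. Working on the log scale does not by itself remove it.

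This is the only planned analysis that links the cellular secondary endpoints to the antibody response, and Template 19 attaches a confidence interval to it. A weak or negative coefficient could be read as evidence that cellular memory contributes little to the anamnestic response.

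**Working it through.** **Inputs from the documents.** Evaluable n is 80 (Protocol 9.3: 100 × 0.80 = 80). The cut-off is 6.2 mIU/ml, half of which is 3.1; results from 6.2 to 7.65 are set to 6.2 (SAP 11.2.4). SAP Figure 2 shows an illustrative log-log regression of Day 30 on pre-challenge with slope 0.935 and R² 0.4976. SAP Annex 3 says its templates were copied from another study, so this slope is not evidence about the present population. The plan gives no figure for the correlation itself, so there is none to reproduce.

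**Inputs assumed.** The true slope m, the correlation ρ of log cell frequency with log pre-challenge anti-HBs, and the true partial correlation p of log cell frequency with log Day 30 at a given pre-challenge level.

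**Algebra, log scale, no flooring.** In units of the pre-challenge SD, write log Day 30 = m·x + residual with residual SD s. Log fold rise is then (m − 1)·x + residual, and

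corr(cells, log fold rise) = [(m − 1)ρ + p·s·√(1 − ρ²)] / √[(m − 1)² + s²].

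From Figure 2, the SD ratio is 0.935/√0.4976 = 1.325, so s = 1.325 × √(1 − 0.4976) = 0.939. With ρ = 0.4 and p = 0.30:

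- m = 0.935: (−0.026 + 0.258)/0.942 = 0.25.
- m = 0.6: (−0.160 + 0.258)/1.021 = 0.10.
- m = 0.6 with p = 0: −0.160/1.021 = −0.16.

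The expected coefficient is zero when p = (1 − m)ρ / [s√(1 − ρ²)], and negative below that. At ρ = 0.4 this threshold is 0.03 for m = 0.935, 0.19 for m = 0.6 and 0.28 for m = 0.4.

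**Simulation, log scale, n = 80, with the floor.** Assumptions: log10 pre-challenge mean 1.2 and SD 0.8 (about 30% below 6.2, set to 3.1); residual SD 0.66; Fisher-z 95% CIs. The adjusted analysis is the partial correlation given log10 pre-challenge anti-HBs and an indicator for <6.2. Each pair of values is for ρ = 0.3 / 0.5.

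| Slope m | Mean unadjusted r, true p = 0.30 | Unadjusted CI wholly below zero, true p = 0 |
|---|---|---|
| 0.5 | 0.148 / 0.056 | 14.6% / 34.3% |
| 0.7 | 0.223 / 0.169 | 6.1% / 10.4% |
| 0.935 | 0.304 / 0.306 | not a concern at this slope |

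The mean adjusted r is 0.307 to 0.331 throughout when p = 0.30. With p = 0 and slopes of 0.5 to 0.7, the adjusted CI lies wholly below zero in 1 to 2% of trials. For scale, a Fisher-z interval around r = 0.30 at n = 80 runs from 0.09 to 0.49.

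**Raw scale.** The plan states no log transformation. A separate simulation on raw values assumed log10 pre-challenge mean 1.5 and SD 0.8, cell log10 SD 0.5, ρ = 0.5 and p = 0.30. The mean planned r was 0.14 at m = 0.935 (negative in 16% of trials) and 0.05 at m = 0.6 (negative in 44%).

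**The case against.** Five points can be made for the plan.

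- **Fold rise is a legitimate target.** A Pearson coefficient with amplitude estimates the association with amplitude as the plan defines it. A reader might infer that the interval in Template 19 would describe the wrong quantity; the documents do not support that. The partial correlation answers a different question, and the simulation takes that question as the truth. This stands, and it is why the planned coefficient should be kept.
- **Reversal.** A reader might also infer that a real positive link is likely to be reported as negative. With a true partial correlation of 0.30 and slopes of 0.5 to 0.7, every mean unadjusted coefficient is positive. The point estimate is negative in up to 31% of trials in the worst case, but the CI lies wholly below zero in under 1%. The 5 to 35% figure applies when there is no link to reverse. Attenuation is the main risk to a real link.
- **The size is assumed.** Neither document gives the slope or the cell-antibody correlation. The only slope shown, 0.935, gives close agreement, but it is mock content and settles nothing either way.
- **Adjustment is not perfect.** Collapsing values below 6.2 to 3.1 leaves some confounding. With no true link, the adjusted CI lies wholly above zero in about 4 to 6% of trials in most scenarios, against 2.5% nominal. The bias is small but should be acknowledged.
- **Low consequence.** The analysis is labelled exploratory, and Protocol 9.10 and SAP 7 make all analyses descriptive. This stands.

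**Conclusion.** The point holds as a conditional weakness of an exploratory analysis. The unadjusted coefficient is pulled downward if the log-log slope is below 1 and cell frequencies correlate positively with pre-challenge antibody. At assumed slopes of 0.5 to 0.7 and correlations of 0.3 to 0.5, a true partial correlation of 0.30 shrinks to about 0.06 to 0.22. With no link, a spurious wholly negative interval appears in about 5 to 35% of trials. At a slope of 0.935 on the log scale, the simulated methods agree closely (0.30 to 0.31 unadjusted, 0.31 to 0.33 adjusted). Where this trial would fall cannot be told from the documents. No primary or secondary conclusion is affected. The change is worth making because the covariate is already collected and adjustment does little harm when the artefact is small.

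**What to change.** In SAP 6.3.1 and Template 19, and in Protocol 9.8, add the partial correlation, with 95% CI, of log10 Day 30 anti-HBs with log10 cell frequency, adjusted for log10 pre-challenge anti-HBs and an indicator for pre-challenge <6.2 mIU/ml. Keep the planned Pearson coefficient, on log fold rise, as a second line.

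In the same edit:

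- Name the cell time-point, with the pre-challenge frequency as the main predictor.
- State that the half-cut-off value (3.1 mIU/ml) also applies to the fold-rise denominator.
- Extend to T cells the 0.5 rule for zeros that Template 16 gives for B cells; Template 15 has no such rule.
- Note that flooring leaves a small upward bias after adjustment.

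The cost is a few sentences and one extra line per cell type in a mock table. If the protocol is not amended, the change can be recorded in SAP 9 and justified in the study report, as Protocol 9.11 requires. No new data, visits or subjects are needed, and the adjustment uses two degrees of freedom out of about 80.

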9.9. Analysis of safety

The primary analysis will be performed on the TVC.

- The percentage of subjects who reported at least one local AE (solicited and unsolicited), with at least one general AE (solicited and unsolicited) and with any AE during the 4-day (Days 0-3) follow-up period after the vaccination will be tabulated with exact 95% CI. The same calculations will be performed for any Grade 3 (solicited or unsolicited) symptoms and any symptoms requiring medical attention.
- The percentage of subjects reporting each individual solicited symptom during the 4-day (Days 0-3) follow-up period with exact 95% CI, by type of AE; by severity (any Grade, Grade 3 only); by relationship to vaccination (any relationship, related only) will be tabulated.
- The occurrence of fever will be tabulated per 0.5°C cumulative increments as well as the occurrence of Grade 3 fever (> 39.0 °C axillary temperature) with causal relationship to vaccination.
- The percentage of subjects reporting at least one report of unsolicited AE classified by the Medical Dictionary for Regulatory Activities (MedDRA) and reported within the 31-day (Days 0-30) follow-up period after vaccination will be tabulated with exact 95% CI. The same tabulation will be performed for Grade 3 unsolicited AEs and for unsolicited AEs with a causal relationship to vaccination.
- SAEs during the entire study period and withdrawals due to AEs and SAEs reported during the 31-day follow-up period after the challenge dose will be described in detail.

9.10. Interpretation of analyses

The analyses will be detailed in a descriptive manner.

9.11. Conduct of analyses

Any deviation(s) or change(s) from the original statistical plan outlined in this protocol will be described and justified in the final study report.

9.11.1. Sequence of analyses

The demographic, immunogenicity and safety analyses of the antibodies and the challenge dose will be performed at the end of the study when all data are available. These analyses will be the basis of a Clinical Study Report and will be made available to the investigator.

9.11.2. Statistical considerations for interim analyses

Interim analyses are not planned for this study.

10. ADMINISTRATIVE MATTERS

To comply with ICH GCP administrative obligations relating to data collection, monitoring, archiving data, audits, confidentiality and publications must be fulfilled.

10.1. Electronic Case Report Form instructions

A validated GSK defined electronic data collection tool will be used as the method for data collection.

In all cases, subject initials will not be collected nor transmitted to GSK. Subject data necessary for analysis and reporting will be entered/transmitted into a validated database or data system. Clinical data management will be performed in accordance with applicable GSK standards and data cleaning procedures.

While completed eCRFs are reviewed by a GSK Biologicals' Site Monitor at the study site, omissions or inconsistencies detected by subsequent eCRF review may necessitate clarification or correction of omissions or inconsistencies with documentation and approval by the investigator or appropriately qualified designee. In all cases, the investigator remains accountable for the study data.

The investigator will be provided with a CD-ROM of the final version of the data generated at the investigational site once the database is archived and the study report is complete and approved by all parties.

10.2. Study Monitoring by GSK Biologicals

GSK will monitor the study to verify that, amongst others, the:

- Data are authentic, accurate, and complete.
- Safety and rights of subjects are being protected.
- Study is conducted in accordance with the currently approved protocol, any other study agreements, GCP and all applicable regulatory requirements.

The investigator and the head of the medical institution (where applicable) agrees to allow the monitor direct access to all relevant documents.

The investigator must ensure provision of reasonable time, space and qualified personnel for monitoring visits.

Direct access to all study-site related and source data is mandatory for the purpose of monitoring review. The monitor will perform an eCRF review and a Source Document Verification (SDV). By SDV we understand verifying eCRF entries by comparing them with the source data that will be made available by the investigator for this purpose.

The Source Documentation Agreement Form describes the source data for the different data in the eCRF. This document should be completed and signed by the site monitor and investigator and should be filed in the monitor's and investigator's study file. Any data item for which the eCRF will serve as the source must be identified, agreed and documented in the source documentation agreement form.

For eCRF, the monitor freezes completed and approved screens at each visit.

Upon completion or premature discontinuation of the study, the monitor will conduct site closure activities with the investigator or site staff, as appropriate, in accordance with applicable regulations, GCP, and GSK procedures.

10.3. Record retention

Following closure of the study, the investigator must maintain all site study records (except for those required by local regulations to be maintained elsewhere) in a safe and secure location. The records must be easily accessible, when needed (e.g. audit or inspection), and must be available for review in conjunction with assessment of the facility, supporting systems, and staff. Where permitted by applicable laws/regulations or institutional policy, some or all of these records can be maintained in a validated format other than hard copy (e.g. microfiche, scanned, electronic); however, caution needs to be exercised before such action is taken. The investigator must ensure that all reproductions are legible and are a true and accurate copy of the original and meet accessibility and retrieval standards, including re-generating a hard copy, if required. Furthermore, the investigator must ensure that an acceptable back-up of the reproductions exists and that there is an acceptable quality control procedure in place for making these reproductions.

GSK will inform the investigator/institution of the time period for retaining these records to comply with all applicable regulatory requirements. However, the investigator/institution should seek the written approval of the sponsor before proceeding with the disposal of these records. The minimum retention time will meet the strictest standard applicable to a particular site, as dictated by ICH GCP, any institutional requirements, applicable laws or regulations, or GSK standards/procedures.

The investigator/institution must notify GSK of any changes in the archival arrangements, including, but not limited to archival at an off-site facility, transfer of ownership of the records in the event the investigator leaves the site.

